The primary objective of this study is to determine the efficacy of administering a course of postoperative oral steroids as a preventative measure against complications/a means of enhancing repair in patients undergoing surgery for proximal hypospadias.

It is our hypothesis that a short course of postoperative steroids will facilitate healing of hypospadias to the degree that it will minimize the risk of wound complications. This hypothesis is based on the known scientific effects of corticosteroids on healing as well as the experience of the senior investigator. It is only through completion of a prospective, double-blinded, randomized, placebo-controlled study that we will be able to clearly and convincingly demonstrate that the risks of wound complications is significantly lowered with steroids to justify their routine use in this patient population.

Relevant prior experience and gaps in current knowledge. Scientific or scholarly background for, rationale for, and significance of the research based on existing literature and how it will add to existing knowledge:

Proximal hypospadias repair is a surgery for males who are born with an abnormally located urethral meatus that can be on the proximal third of the shaft of the penis, at the penoscrotal junction, in the scrotum, or on the perineum. With this procedure, a urethra is constructed and pathologic penile curvature is corrected in order to relocate the meatal opening to the glans penis. The goals of hypospadias surgery are to allow for normal function of the penis, which includes the ability to void a straight, non-obstructed urinary stream without spray or dribbling, to have a straight erection, and to propel ejaculate, with a normal penile appearance.

Unfortunately, proximal hypospadias repair has a relatively high postoperative complication rate (reports range from 12-60% with a sum 207/677 [31%] from: Aoki, 2008; Bush, 2013; Braga, 2007; Chuang, 1995; Ghanem, 2011; Gopal, 2008; Hayashi, 2007; de Mattos e Silva, 2009; Powell, 2000; Shukla, 2004; Snodgrass, 2011). The known complications include fistula formation, glans dehiscence, wound breakdown, meatal stenosis, urethral stricture formation, diverticula formation, and meatal retraction with a poor cosmetic result, and all of these require surgical treatment under general anesthesia.

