The type of hypospadias repair will be determined by the surgeon in the operating room at the time of the surgery based on the clinical scenario. Children will be excluded if they are found upon the exam under anesthesia in the operating room at the time of surgery not to have proximal hypospadias. The final severity of the hypospadias will be documented by the surgeon based on an examination performed in the operating room under anesthesia just prior to initiation of the surgical repair. The need for short-term postoperative stenting will be decided at the time of the procedure. After the procedure, the pharmacy will deliver the medication, prednisolone versus placebo which will be blinded from the parents as well as the surgeon, to the OR and the surgeon will bring the medication to the families after surgery. At that time the parents are instructed on how to administer the steroid or placebo, twice daily for 5 days. This constitutes the focus of the study and is the only variation from standard treatment. Parents will be instructed to call for any suspected adverse reaction to the medication versus placebo and for any findings consistent with glans dehiscence, wound breakdown, fistula formation, diverticulum formation, meatal stenosis, or urethral stricture.

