All patients will be seen by the surgeon in postoperative follow up in the Urology Outpatient Clinic 7-12 days after the surgery following completion of the 5-day course of prednisolone versus placebo. Stents will be removed at this time as is standard practice. The next follow up will be at 4 to 12 weeks postoperatively as is standard practice. At a minimum, participants will be asked to follow up again at 6-months postoperative, and after toilet training, and possibly one year after puberty up until 16 years of age, which does not deviate from standard practices. Each postoperative visit will include evaluation for glans dehiscence, wound breakdown, fistula formation, diverticulum formation, the presence of meatal stenosis, the presence of a urethral stricture, and the location of the urethral meatus/cosmetic appearance of the phallus in addition to the quality and progression of wound healing and the quality of the urinary stream. Any phone calls, emergency room, or office visits that take place outside of the scheduled follow-up visits will be tracked so that a phone or office interview can be arranged to make similar assessments if they are not made at the time of those encounters. Any return to the operating room for redo-hypospadias surgery as well as the intraoperative physical exam and findings will be noted. Any adverse events associated with the medication or placebo will be noted and classified in terms of severity, expectedness, and association with the medication or placebo.

Data will be stored in RedCap, a secure server with de-identified patient information that can be accessed only by investigators on the study using their individualized usernames and passwords. Data analysis will be made on at least an annual basis to allow for early termination of the study in the case that one arm is unequivocally superior or inferior.

Power analysis used and method of statistical analysis:

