We will need to enroll 64 patients in the study to reject a false null hypothesis if we assume that the complication rate for proximal hypospadias surgery is 30% and that the administration of prednisolone for five-days postoperatively at a dose of 1.5 mg/kg/day divided into two doses will decrease that rate to 5%. We will need to enroll 196 patients in the study to reject a false null hypothesis if we assume that the complication rate for proximal hypospadias surgery is 25% and that the administration of prednisolone for five-days postoperatively at a dose of 1.5 mg/kg/day divided into two doses will decrease that rate to 10%. For this reason, we would like to accrue roughly 200 patients in the study, however, we will run statistical analyses at least yearly so that the study can be concluded early if indicated.

Patients will be randomized by the research pharmacist with help from the statisticians at the Clinical and Translational Science Institute (CTSI) here at the University of Pittsburgh. The research pharmacist at Children's Hospital of Pittsburgh will blind the researchers/surgeons to the identity of the oral solution (steroid versus placebo) being administered. The placebo group will serve as the study control to determine the change in complication rate achieved through the use of steroids.

Statistical Analysis Plan:

Demographic measures (median gestation, weight, follow-up in months, incidence of NICU stay, and incidence of comorbidities) will be compared between the steroid and placebo arms using appropriate statistical approach, i.e., t-tests, Fisher's Exact test, or Wilcoxon Rank-sum test.

We were unable to meet our enrollment goal sufficient to test our hypothesis for each complication (meatal retraction, meatal stenosis, glans dehiscence, skin breakdown along suture lines, urethra breakdown proximal to glans, urethrocutaneous fistula, suspected stricture, and suspected urethral diverticulum), therefore the incidence of complication overall between the steroid and placebo groups will be analyzed using Fisher's Exact Test.

Likewise, Fisher's Exact Test will be used to test the quality of wound healing, including the location of the urethral meatus (subcoronal, distal shaft, proximal shaft, penoscrotal, scrotal perineal, and other), and the improvement of chordee (resolved/ improved/ described but not documented/ no improvement/ not described) in each category (degloving, ventral, and plication).

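### Two record-status codes are tested as chordee outcomes at an unstated time, and the meatal location scale has no level for the glans, the target of the repair

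*Combined protocol and SAP*

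**What the plan says.** **Statistical Analysis Plan.** One sentence applies Fisher's Exact Test to wound-healing quality. Its first item is "location of the urethral meatus (subcoronal, distal shaft, proximal shaft, penoscrotal, scrotal perineal, and other". Its second item, for chordee, reads "improvement of chordee (resolved/ improved/ described but not documented/ no improvement/ not described) in each category (degloving, ventral, and plication". The grammar allows chordee to be part of wound healing or to stand beside it. The sentence gives no visit, no ordering of levels and no rule for unrecorded values. The preceding paragraph says "We were unable to meet our enrollment goal sufficient to test our hypothesis for each complication (meatal retraction", and so on through the list, and therefore pools complications into one overall comparison. Meatal retraction is one of its components.

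**Relevant prior experience and gaps in current knowledge.** In the repair, "a urethra is constructed and pathologic penile curvature is corrected in order to relocate the meatal opening to the glans penis". The goals of surgery include "to have a straight erection".

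**Detailed description of all research activities.** Children are excluded if found "at the time of surgery not to have proximal hypospadias". Study drug comes later: "After the procedure, the pharmacy will deliver the medication, prednisolone versus placebo". On follow-up, the protocol says: "Each postoperative visit will include evaluation for glans dehiscence, wound breakdown, fistula formation, diverticulum formation, the presence of meatal stenosis". That list goes on to meatal position, cosmetic appearance, wound healing and urinary stream, but does not name chordee or curvature.

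**Primary and secondary study endpoints.** The second aim is wound-healing quality, with meatal location as its example. Chordee is not named here either.

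**The concern.** A between-arm test should compare what happened to the child. Two chordee levels instead record whether something was written down. With no rule removing them, a chance imbalance in charting can produce a small p-value, and balanced charting gaps can dilute a clinical difference.

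The missing time point decides whether the test means anything. Curvature is corrected during the operation and drug arrives afterwards, so an intraoperative grade cannot respond to treatment.

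For meatal location, the one result that the operation aims for has no level of its own. The plan as written would not yield the proportion of boys in each arm whose meatus ended on the glans, although meatal location is its own example of the second aim.

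**Working it through.** The plan states no figure for these tests, so there is none to reproduce. The documents give no outcome distributions. All distributions below are assumed, as are two-sided alpha of 0.05 and 1:1 allocation. Group sizes of 32 and 98 per arm are half of the 64- and 196-patient scenarios in the power section; 50 per arm is an assumed intermediate.

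**1. What the record codes do to a p-value.** Exact r x 2 Fisher (Fisher-Freeman-Halton) test, 32 per arm, levels in the SAP's order (resolved / improved / described but not documented / no improvement / not described):

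| Assumed counts | All five levels | Three clinical levels |
|---|---|---|
| 12/4/0/4/12 vs 12/4/7/4/5 (clinical results identical) | p = 0.034 | p = 1.00 |
| 16/3/4/2/7 vs 8/5/4/8/7 (record codes identical) | p = 0.150 | p = 0.030 |

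**2. If chordee was scored at surgery.** Every significant result is then chance. For three tests at 5% each, the bound under any dependence is 3 x 0.05 = 15%. Independence would give 1 - 0.95^3 = 14.3%, but the three categories (degloving, ventral, plication) may come from the same children, so 15% is the safe statement.

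**3. If chordee was scored after surgery.** Assumed resolved/improved/no improvement: 65/20/15% vs 80/13/7%. The undocumented share is equal in both arms, split equally over the two codes and unrelated to outcome (8,000 simulated trials per cell). Power with codes kept vs set to missing:

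| Undocumented | 98 per arm | 50 per arm | 32 per arm |
|---|---|---|---|
| 10% | 43.2% vs 52.0% | 23.7% vs 28.1% | 16.1% vs 18.3% |
| 20% | 36.9% vs 48.4% | 19.6% vs 24.8% | 13.8% vs 16.8% |
| 40% | 27.3% vs 35.9% | 14.5% vs 19.3% | 10.0% vs 12.1% |

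The losses are 8.6-11.5, 4.4-5.2 and 2.1-3.0 points. Steps 2 and 3 are alternatives and do not add.

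**4. If documentation is linked to outcome.** Keep the same clinical rates, but let 50% of resolved and 10% of other cases be *not described* (one code, 2,000 trials). Power with the code kept vs set to missing is 44.6% vs 45.1%, 20.6% vs 22.6% and 15.5% vs 15.1% at 98, 50 and 32 per arm. The gain essentially vanishes. The documented-case rates also shift:
- Control: resolved and documented 65% x 0.5 = 32.5%; all documented 32.5% + 35% x 0.9 = 64%; apparent resolution 32.5/64 = 50.8% (true 65%).
- Steroid: 80% x 0.5 = 40%; 40% + 20% x 0.9 = 58%; 40/58 = 69.0% (true 80%).

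The apparent difference is 18.2 points against a true 15. Dropping the codes is therefore not automatically safe.

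**5. Meatal location.** If *other* holds only glans cases, relabelling it leaves Fisher's p-value unchanged; the loss is in what can be reported. Assumed control distribution, glans/subcoronal/distal shaft/proximal shaft/penoscrotal/scrotal perineal: 70/12/8/5/3/2% (6,000 trials per six-level cell; 2x2 power exact).
- Steroid arm 70/6/14/5/3/2%, equal success: the six-level test rejects in 28.4%, 17.1% and 12.1% of trials at 98, 50 and 32 per arm; glans yes/no rejects in 3.5%, 3.1% and 2.8%.
- Glans 70% vs 84% at 98 per arm: yes/no has 58.4% power. The six-level test has 42.2% if failures are 7/4/2.5/1.5/1% and 95.8% if they are 0/6/5/3/2%.

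Neither test is always the more powerful. They answer different questions, and only yes/no asks whether the repair reached its target.

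**The case against.** **The meatal list could be the presenting site.** The protocol documents initial degree at the first visit and final severity just before repair. This reading cannot be ruled out. It fits poorly, because the intraoperative exclusion leaves little use for subcoronal and distal-shaft levels, and because the SAP puts the list under wound healing while the protocol assesses meatal position at every postoperative visit. If it is right, the variable precedes drug and is not an efficacy outcome, so the text still needs correcting.

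**The 28% rejection rate is not a false-positive rate.** A reader might infer that it is. In that example the arms truly differ in location, so rejection is correct for the hypothesis tested. What stands is only that such a rejection says nothing about success.

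**The larger power losses belong to an enrolment that was probably not reached.** This stands in part. The SAP reports a shortfall without giving the number, and at 50 or 32 per arm the loss is 2-5 points.

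**The codes may carry outcome information.** This also stands: a straight result may simply have drawn no comment. The documents do not define the codes, so they must be defined before they are set to missing.

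**Failure is already counted.** Meatal retraction is in the overall complication comparison, so failed meatal position is partly captured there.

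**Conclusion.** The concern holds in limited form. Two things are wrong as written: record-status codes act as outcome levels, and a postoperative meatal scale omits the surgical target. The unstated time of scoring alone would be missing detail, but here it decides whether the chordee tests can inform efficacy at all.

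Three stronger conclusions are not supported:
- That chordee was certainly scored at surgery. The category labels and the silence of the endpoint and visit lists suggest it. A straight erection as a goal, and cosmetic assessment at each visit, leave postoperative scoring possible.
- That the codes bias the comparison. Randomisation is blinded, so the expected effect of charting gaps unrelated to outcome is dilution; the p = 0.034 example shows what an imbalance can do, not a systematic tendency.
- That the main result is compromised. The overall complication comparison does not use either scale.

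The power figures rest on assumed distributions and, for the gain from removing the codes, on documentation being unrelated to outcome. The textual defects do not depend on them. The weight lies between a minor clarification and a change that should be made before analysis.

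**What to change.** - **Chordee, if scored at surgery:** say so, report it by degloving, ventral and plication as an operative characteristic, and drop the efficacy test.
- **Chordee, if scored after surgery:** name the visit, define the two record codes, test resolved/improved/no improvement in documented cases, report code counts by arm, and add a sensitivity analysis counting *not described* as resolved.
- **Meatal location:** state that it is postoperative and name the visit. Add a glans level and recode *other* from visit notes by someone blinded to arm. Compare glans yes/no with Fisher's Exact Test and a confidence interval for the difference, and describe the remaining levels by arm.
- **Labelling:** mark these changes as made late, since the SAP text already reports the enrolment shortfall and the protocol plans at least yearly analyses.

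The cost is SAP wording and some chart recoding, with no new patients or procedures. The documents do not show whether the notes permit recoding; cases that cannot be recoded become missing. The documented-case analysis keeps its assumption that documentation is unrelated to outcome, which the sensitivity analysis probes but does not remove.
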